- The Subject Dosing Diary and the Parkinson's Disease Diary will be completed by the subjects or their caregivers for the 3 consecutive days prior to each visit. ö
- It is up to the discretion of the Investigator to determine how many titration days are necessary to obtain optimal clinical response.

р.

- The Sleep Attacks Questionnaire will be used to screen for sleep attacks. Results should be recorded in source but will not be entered in the clinical database. 4
- The "Baseline/Screening" C-SSRS will be the first assessment scale administered to the subject. At each subsequent visit, the "Since Last Visit" C-SSRS scale should be administered.
- The subject's expected time of peak dose dyskinesia should be determined during screening and the UDysRS should be administered at this time throughout the study ò
- morning prior to the subject taking their first daily dose of anti-PD medication. At a minimum a subject should be 8 hours without anti-PD medication before the UPDRS is completed. The best "On" time rating should be done approximately 1 to 2 hours post any morning dose of study drug or PD medications but prior to lunch. If possible, the UPDRS should be done at the same time of day throughout the trial. The "Off" time UPDRS Part III will only be done during Screening; all other UPDRS assessments will During Visit 1 the UPDRS Part III will be done during practically defined "Off" time and best "On" time. The practically defined "Off" time UPDRS will be done in the
- The mAIMS should be completed following the UDysRS at the subject's expected time of peak dose dyskinesia. 'n.

All applicable clinical, safety, health outcome and cognition assessments will be administered only by individuals qualified by the Sponsor. Note:

5.3.1.1 **Study Procedures**

The study procedures outlined in Table 4 are discussed in this section, with the exception of the collection of adverse event information and product complaints (Section 6.0).

Due to the length of assessments on Visit 1, assessments may be performed over multiple days.

Informed Consent

Voluntary written informed consent must be obtained from each subject (and if appropriate, their caregiver) by the Investigator prior to performing any study-related procedures. Consenting will be performed according to local regulations.

Subject Medical and Neurological History

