During the Screening Period, subjects should be asked to answer these questions based on their experiences during the 3 months prior to Screening Visit 1. During the Screening Period, if the subject is currently or has been recently experiencing sleep attacks, they will be excluded from participation in the study and referred for appropriate follow-up care if the Investigator feels these are clinically significant. The assessment of Sleep Attacks completed at the Screening Visit 1 will serve as baseline for clinical assessment.

EudraCT 2016-001403-23

Physical Examination

At Screening V1, V2 (optional visit) and Randomization V3 a full physical examination will be performed. Symptom-driven physical examinations will be performed at subsequent visits.

Neurological Examination

A Neurological Examination including light touch and pinprick sensation, vibratory sensation, deep tendon reflexes, and strength assessments will be performed at the times indicated in Table 4. The Neurological Examination should be bilateral and be done during the subject's "On" time.

Any abnormalities or symptoms identified at Visits 1, 2 and 3 will not be recorded as adverse events but will be recorded in Medical History eCRF. Any new abnormalities or symptoms that change in severity or frequency following randomization for the OMT group and the first dose of IP for the LCIG treatment group will be recorded as adverse events.

The Neurological Examination will assess:

- Cranial nerves assessment of cranial nerves II XII, including fundoscopic examination
- Motor system assessment of tone, strength and abnormal movements
- Sensory system including light touch, pinprick, joint position and vibratory sense
- Reflexes assessment of deep tendon reflexes and plantar responses (Babinski
- Coordination assessment of upper and lower extremities
- Gait assessment of base and tandem gait

The Neurological Examination performed at Visit 1, will serve as baseline for clinical assessment.

Dermatological Assessment

A comprehensive assessment by an experienced dermatologist for the presence of any suspicious skin lesions and subsequent evaluation for melanoma will be performed prior to V3 and at Week 12/Premature Discontinuation. If a suspicious lesion is present, a biopsy should be obtained for proper diagnosis and confirmation that lesion does not meet exclusion criteria.

Positive screens will be exclusionary.

GI Examination

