5.3.4 Safety Variables

Safety and tolerability over the course of the study will be assessed by the following measurements:

- Adverse event monitoring
- Neurological exams
- Clinical laboratory evaluations

- Electrocardiogram
- Vital signs and weight
- Columbia Suicide Severity Rating Scale (C-SSRS)
- Minnesota Impulsive Disorders Interview (MIDI)
- Sleep Attacks Questionnaire

Removal of Subjects from Therapy or Assessment 5.4

5.4.1 **Discontinuation of Individual Subjects**

Each subject has the right to withdraw from the study at any time. In addition, the Investigator may discontinue a subject from the study at any time if the Investigator considers it necessary for any reason, including the occurrence of an adverse event or noncompliance with the protocol. Subjects who withdraw from the study will not be replaced.

Subjects may develop adverse events or abnormalities in vital signs, ECGs, physical examinations, neurological examinations or laboratory determinations during their participation in the study. If these occur, the Investigator may discontinue a subject from the study if, in their clinical judgment, continued participation would result in undue risk or further worsening of the condition.

The following adverse events require Premature Discontinuation:

- Subjects who develop a melanoma during the course of the study should be discontinued from participation and referred for appropriate follow-up care
- Subjects who develop impulsive behavior that is clinically significant, in the judgment of the Investigator, should be discontinued from participation in the study and referred for appropriate follow-up care
- As indicated by answering yes to question 4 or 5 on the C-SSRS, subjects should be discontinued from participation in the study and referred for appropriate follow-up care

• Subjects who become pregnant should be discontinued from participation in the study and referred for appropriate follow-up care

In the event that a subject withdraws or is discontinued from the study after they have begun the PEG-J placement procedure, the assessments for an End of Treatment/Week 12 (V8) should be performed as soon as possible.

If a subject is discontinued from the study with an ongoing adverse event or an unresolved laboratory result that is significantly outside of the reference range, the Investigator will attempt to provide follow-up until a satisfactory clinical resolution of the laboratory result or adverse event is achieved.

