4.6 Safety Measures

Safety and tolerability over the course of the study will be assessed by the following measures.

- Adverse event monitoring
- Neurological exams
- Clinical laboratory evaluations
- Electrocardiogram
- Vital signs and weight
- Columbia Suicide Severity Rating Scale (C-SSRS)
- Minnesota Impulsive Disorders Interview (MIDI)
- Sleep Attacks Questionnaire (SAQ)

A description of each measure is included in Protocol Section 5.3.1.1 Study Procedures. Each measure will be assessed at the times indicated in the study activities flow chart (Appendix A).

5.0 **Analysis Populations**

Analyses will be performed utilizing the following datasets.

Intent-to-Treat Dataset

The intent-to-treat dataset will include all subjects who are randomized to the optimized medical treatment, and all subjects who are randomized to LCIG and received at least one dose of study drug following PEG-J placement. The intent-to-treat dataset will be used to summarize efficacy and health outcome measures.

Safety Dataset

The safety dataset will include all subjects who are randomized to the optimized medical treatment, and all subjects who are randomized to LCIG and have a study device (NJ and/or PEG-J) placement procedure. The safety dataset will be used to summarize safety data during the OMT and LCIG treatment period.

6.0 **Analysis Conventions**

6.1 **Statistical Significance**

This is a randomized open-label study. Unless otherwise specified, statistical tests will be two-sided and the null hypothesis will be rejected at the significance level of $\alpha = 0.050$. *P* values will be rounded to three decimal points before assessing statistical significance. If the primary efficacy variable UDysRS total score is statistically significant, each of the secondary efficacy variables will be tested using the fixed sequence below as a gatekeeping procedure and at α level of 0.050. Testing will cease at the point that a secondary variable fails to demonstrate statistical significance.

"ON" time without troublesome dyskinesia as measured by the PD Diary

- Parkinson's Disease Questionaire-8 (PDQ-8) summary index
- Clinical Global Impression of Change (CGI-C) Score
- UPDRS Part II Score
- "OFF" time as measured by the PD Diary
- UPDRS Part III Score

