6.5 Analysis by Planned Visit for Non-Diary Variables

A midpoint convention will be used to assign all observations to a planned visit based on the Study Day of the observation. If there are multiple observations on the same day, the average will be taken and considered the observation for the day. If more than one observation is assigned to a planned visit, the last observation will be selected and considered the observation for the planned visit.

The following Study Day windows will be used to assign efficacy and health outcome assessments to planned study visits during the 12-week Treatment Period. Assessments

on the day of first day of LCIG infusion via PEG-J are not planned and will not be included in the analysis.

Assessment	Planned Visit	Nominal Study Day	Study Day Range ^a
UDysRS, UPDRS,	Baseline		\leq date of randomization
mAIMS, CGI-C	Week 2	14	2 - 21
	Week 4	28	22 - 42
	Week 8	56	43 - 70
	Week 12	84	≥ 71
PDQ-8	Baseline		\leq date of randomization
	Week 8	56	2 - 70
	Week 12	84	≥ 71
King's PD Pain Scale	Baseline		\leq date of randomization
	Week 4	28	2 - 42
	Week 8	56	43 - 70
	Week 12	84	≥ 71

a. For subjects in LCIG group, all post-baseline assessments must also be after start of LCIG infusion through PEG-J and no more than 1 day after the date of the last LCIG infusion in the 12-week Treatment Period.

The following Study Day windows will be used to assign safety assessments during the
12-week Treatment Period to planned study visits.

Assessment	Planned Visit	Nominal Study Day	Study Day Range ^a
Vital signs and weight,	Baseline		\leq date of randomization
MIDI, Sleep Attacks	Week 2	14	2 - 21
Questionnaire, C-SSRS	Week 4	28	22 - 42
	Week 8	56	43 - 70
	Week 12	84	≥ 71
	Week 13 FU ^b	91	$2 \leq RxEnd Days$
Clinical labs and	Baseline		\leq date of randomization
Electrocardiograms, Special labs	Week 8	56	1 - 70
Special laus	Week 12	84	≥ 71

For subjects in LCIG group, all post-baseline assessments must also be no more than 1 day after the final PEG-J a. removal for subjects who do not transit to commercial product or no more than 1 day after the final Study M15-535 LCIG infusion during 12-week Treatment Period for subjects who transit to commercial product.

b. Applicable only to LCIG subjects who will not continue on commercial product.

For LCIG subjects who enter the Transition Period, vital signs and weight, special labs, C-SSRS and MIDI will be assessed every 12 weeks.

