10.4 Analysis of Vital Signs and Weight

Vital sign variables include: body temperature, pulse (sitting, standing and orthostatic), diastolic blood pressure (sitting, standing and orthostatic), and systolic blood pressure (sitting, standing and orthostatic).

Weight variables include: weight and BMI.

Orthostatic variables will be calculated as the change from sitting to standing (standing measurement minus sitting measurement).

BMI will be calculated using height as measured during screening.

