10.6 Analysis of Sleep Attack Questions

At Screening Visit 1, the sleep attack questions will collect history during the previous 3 months. At all other visits, the sleep attack questions will collect experience since the last visit. Affirmative responses to the sleep attack questions will be summarized by treatment for the study period on or before the date of randomization and for the study period on or after Day 1.

Each summary will include the number and percentage of subjects in each treatment group reporting a) 1 or more sleep attacks at any visit, b) 1 or more sleep attacks at any visit without sleepiness or drowsiness prior to sleep attack, and c) 1 or more sleep attacks at any visit with bad outcome during the 12-week Treatment Period. The highest number of sleep attacks reported at any visit (1, 2, 3, more than 3) will also be summarized by the number and percentage of subjects in each treatment group with each count.

A listing will also be prepared that includes all subjects who reported 1 or more sleep attacks at any visit.

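### SAP 10.6 tabulates sleep-attack answers that the protocol keeps out of the database, and SAP 10.4 analyses sitting readings that the protocol does not take (minor, safety reporting only)

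*Protocol*

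**What the plan says.** **Sleep attacks.** Protocol 5.3.1.1 schedules the questionnaire at the visits marked in Table 4: V1, optional V2, V3, V5 to V8, and V9 for LCIG subjects who stop. The Table 4 note then says: "Results should be recorded in source but will not be entered in the clinical database". Protocol 5.3.4 includes the questionnaire in the list headed "Safety and tolerability over the course of the study will be assessed by the following measurements", and 5.3.1.1 adds: "The assessment of Sleep Attacks completed at the Screening Visit 1 will serve as baseline for clinical assessment". The planned safety summaries do not include it. The synopsis names adverse events, laboratory tests, vital signs and weight, special labs, C-SSRS and MIDI, and section 8.1.4.6 covers only MIDI and C-SSRS.

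The SAP treats the answers as analysis data. Section 4.6 lists the questionnaire as a safety measure, and the 6.5 safety windows include a row containing "MIDI, Sleep Attacks". Section 10.6 states: "Affirmative responses to the sleep attack questions will be summarized by treatment for the study period", meaning one period up to randomisation and one from Day 1. Section 12.0 says the SAP changes nothing from Protocol Amendment 1.

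**Posture.** Protocol 5.3.1.1 takes blood pressure and pulse supine (after 3 to 5 minutes) and standing (after 2 minutes). SAP 10.4 lists "pulse (sitting, standing and orthostatic), diastolic blood pressure (sitting, standing and orthostatic), and systolic blood pressure (sitting, standing and orthostatic" and then states: "Orthostatic variables will be calculated as the change from sitting to standing (standing measurement minus sitting measurement". SAP Appendix C sets its blood pressure limits on supine and standing readings and its orthostatic limits on the fall from supine to standing.

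**The concern.** Two planned sets of safety output appear to have no input. Protocol 3.2 names sudden onset of sleep and orthostatic hypotension as important identified risks, so a programmer should not have to guess at either.

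For sleep attacks, the question is whether the SAP 10.6 tables can be filled at all. For vital signs, it is whether the sitting and orthostatic mean changes in SAP 10.4.1 can be computed from what sites measure. Empty or mislabelled tables would be found only at programming, close to database lock.

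**Working it through.** The plan gives no figure to reproduce. The check sets the texts side by side and counts what each conflict touches.

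**(a) Questionnaire**

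1. Data rule: Protocol Table 4 note, source only.
2. What SAP 10.6 needs by arm: any attack; any attack without prior drowsiness; any attack with a bad outcome; the highest count at a visit (1, 2, 3, more than 3); and a subject listing. That is four kinds of tabulation plus one listing, 4 + 1 = 5. All need item-level answers, and the items match the questions in Protocol 5.3.1.1.
3. If the note holds, none of the 5 has data, and the SAP 6.5 windows have nothing to assign.
4. What remains is adverse-event reporting:
   - Protocol 6.1 records events raised by a query, so a positive answer can become an adverse event.
   - Protocol 6.5 collects all adverse events from randomisation. Before that it collects only serious and protocol-related non-serious events.
   - In the LCIG arm, treatment-emergent events start at initial tube placement. Events between randomisation and placement are summarised separately (Protocol 8.1.4.2, SAP 10.2.1).
5. What would be lost: prior drowsiness, bad outcome and count as structured items, and the pre-randomisation summary. That summary would hold mainly attacks judged not clinically significant, because clinically significant ones are exclusionary (Protocol 5.2.2 criterion 10, and 5.3.1.1).

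**(b) Posture**

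| Text | Postures used |
|---|---|
| Protocol 5.3.1.1, pulse and blood pressure | supine, standing |
| SAP 10.4, pulse and blood pressure | sitting, standing |
| SAP Appendix C, blood pressure | supine, standing |
| SAP Appendix C, pulse rate | none stated |

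1. Variables listed in SAP 10.4: temperature 1 + three measures × three forms 9 + weight 1 + BMI 1 = 12.
2. Variables needing a sitting value: 3 sitting + 3 orthostatic = 6 of 12.
3. Occurrences of the word: 3 in the variable list + 2 in the derivation = 5.
4. Appendix C has an orthostatic criterion for systolic and diastolic pressure, 2 of the 3 orthostatic variables. Orthostatic pulse has none, so its only planned analysis is the mean change that cites sitting.

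**Entry cost for (a).** 60 subjects × 6 visits (V1, V3, V5, V6, V7, V8) = 360 forms if all attend. Add 0 to 60 at optional V2 and 0 to 30 at V9, which applies only to LCIG subjects.

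**The case against.** The strongest reply is that nothing need be lost. The SAP is dated 21 May 2018, two years after Amendment 1 of 26 May 2016, and its 10.6 follows the questions item by item. The eCRF may capture the answers, in which case the protocol note is simply out of date. The documents do not include the eCRF, and the matching note in SAP Appendix A is not legible in the text reviewed, so this cannot be excluded. It stands as a reason to check the eCRF before anything else. It does not remove the conflict: one of the two texts still needs correcting.

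Three stronger readings are tempting, and the documents do not support them.

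- *The protocol contradicts itself, because a named safety variable with a baseline is kept out of the database.* This is overstated. The questionnaire is described as a screening and monitoring tool, and such a tool can stay in source while events are reported as adverse events. The baseline phrase is also used for the neurological examination. The planned analyses in the protocol consistently leave the questionnaire out. The real conflict is SAP 6.5 and 10.6 against one protocol note.
- *Sleep attacks would go unreported.* They would not. All adverse events are collected from randomisation, and SAP 10.2.2 tabulates treatment-emergent events by arm.
- *The SAP has chosen a different orthostatic method.* Nothing suggests so. The protocol procedure and Appendix C show the intended posture for blood pressure, and the Appendix C limits on orthostatic pressure falls remain usable. For pulse, only the protocol procedure supplies the posture.

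**Conclusion.** Both contradictions are in the text and the plan is wrong as written, but the matter is minor. It affects safety reporting only. Neither risk is an adverse event of special interest.

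For (a), the loss of all SAP 10.6 outputs depends on the note having been followed in the database build, which the documents do not show. If it was, by-arm sleep-attack reporting falls back on adverse events, without the structured detail and without a pre-randomisation summary.

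For (b), the literal reading leaves 6 of 12 variables without input. It is a wording error with a recoverable meaning, and it rests on the assumption that sites measure posture as the protocol says.

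**What to change.** Settle all of this before database lock.

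1. **Check the eCRF** for the questionnaire answers.
   - If they are captured, correct the Table 4 note. No data entry is needed.
   - If not, amend the note and enter the answers already held in source. The cost is about 360 short forms, plus optional V2 and LCIG-only V9, and a protocol amendment with ethics review where Protocol 9.1 requires it. A new eCRF page may also be needed, which the sponsor would validate under Protocol 10.2.
   - Failing that, delete SAP 10.6 and the questionnaire's entry in SAP 6.5. State in SAP 4.6 that it is a source-only monitoring tool and that sleep attacks are reported from adverse events. This costs wording only.
2. **In SAP 10.4, replace the word sitting with supine in all 5 places**, so that orthostatic change is standing minus supine. The basis is Protocol 5.3.1.1 for pulse and blood pressure, and Appendix C for blood pressure only. The cost is five words.
3. **Clerical, in the same edit:** SAP 10.3.3 should cite Appendix B (laboratory limits) and SAP 10.4.3 should cite Appendix C (vital signs and weight). The two references are swapped.

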5.3.1.2 Rater Requirements

All applicable clinical, safety, health outcome and cognition assessments will be administered only by individuals qualified by the Sponsor. Every effort must be made by the investigative sites to ensure that each subject is rated by the same rater throughout the subject's participation in the study.

Prior to administration of respective scale(s), designated raters will be trained on and certified (if appropriate) in the use of all the scales used in this study. The objective of this certification/training is to ensure uniformity across sites in the administration and scoring of these assessments.

Site Rater Training Requirements

The study scales/questionnaires will be administered only by individuals qualified by the Sponsor and the rater training vendor. The UDysRS Parts 1 and 2 will be assessed and scored by site raters who are qualified based on MDS training. Prior to administration, designated raters (Investigator or an experienced and qualified study site assigned by the Investigator) will be trained and where applicable certified in the use of the study scales/questionnaires. The objective of this certification/training is to ensure uniformity across sites in the administration and scoring of the scale.

The Sponsor, in conjunction with the rater training vendor, will determine the minimum rater qualifications for the rating scale. All raters must meet these qualifications prior to participation in the training process. The names and qualifications of all site personnel to be involved in rating scale and/or administration will be submitted for approval upon site selection. The qualifications of the raters will be verified through the rater training vendor. Qualified raters will be trained and where appropriate tested for competency and, if they meet established requirements, will be certified. Individual exceptions to these requirements must be approved by the Sponsor via the rater training vendor.

Only those persons who have been trained and certified as raters for this study may rate the subjects. Raters who cannot participate in the initial study certification/training or

who become involved in the study at a later time will not be permitted to perform study ratings until they have satisfactorily completed an individualized certification/training program designed by the rater training vendor, approved by the Sponsor, and supervised by the Investigator or his/her designee. It is the responsibility of the Investigator to ensure the raters at his/her site are appropriately trained and certified to administer the selected rating scales. Raters will be reassessed periodically throughout the study.

Blinded Central Rater Training Requirements

The objective portion of the UDysRS (Parts 3 and 4) will be assessed and scored by experienced blinded central raters who are qualified based on MDS training.

The blinded central raters will be blinded to the study protocol and the tested hypotheses and will not have access to the results of other study assessments or medical records for the subject and will not participate in the care or management of the subject. Each rating is based exclusively on a video recording of the interview with the subject.

The blinded central rater will score the UDysRS assessment at the times indicated in Table 4 with the baseline assessment occurring at Visit 3.

5.3.1.3 **Ancillary Support**

Sites will be appropriately trained and provided support on the initiation and titration of LCIG treatment prior to subject enrollment of the first subject at each site.

Duodopa Nurse Specialist (DNS)/AbbVie Duodopa Specialist (ADS)/Nurse Educator (NE)

The Sponsor may provide ancillary support to the study sites by utilizing a Duodopa Nurse Specialist (DNS) to provide additional training to the Investigator and site personnel. DNS services and training are methods of support in the implementation of the LCIG administration system at clinical sites.

The functions of the DNS may include:

- Provide ongoing education and support to the site personnel (Investigator, gastroenterologist or interventional radiologist, study coordinators, research nurses, titration nurses and additional staff) throughout the enrollment period, initiation, titration and rest of the clinical trial
- Facilitate the implementation of the "Train the Trainer Model" by providing initial training to site staff. The Investigator or the appointed delegate may provide ongoing training to new staff.
- Educate the research site staff on medication, cassettes, basic/intermediate/advanced pump function, programming, troubleshooting, tubing, and stoma care
- Educate site personnel (e.g., nurses and physicians) in the proper handling, "Best Practices" for placement, and management of PEG-J tube
- Educate site personnel about Product Complaints and Adverse Events
- Meet local state and hospital/institution rules, laws, and regulations in regards to their role and responsibilities

5.3.2 **Drug Concentration Measurements**

No drug concentration measurements will be completed during the study.

5.3.3 **Efficacy Variables**

5.3.3.1 **Primary Efficacy Variable**

The primary efficacy variable will be the change from baseline to Week 12 in UDysRS Total Score.

The UDysRS was chosen for the assessment of the primary endpoint because it was developed specifically for the assessment of dyskinesia in PD and is endorsed by the International Parkinson and Movement Disorder Society.²⁴ Containing both selfevaluation questions by the patient alone and physician-assessed items to objectively rate dyskinesia and off-dystonia, its clinimetric properties are excellent²³ and it has been

EudraCT 2016-001403-23

demonstrated to be superior for detecting treatment effects compared to other available dyskinesia scales.²⁴

